Study Protocol and Statistical Analysis Plan:

Evidence of the Advantages of Preoperative Intra-aortic Balloon Pump in Surgical Revascularization of Acute Myocardial Infarction

Brief Title: Use of Intra-aortic Balloon Pump Before Surgery for Acute Myocardial Infarction

NCT number: NCT06468982

Document date: May 1, 2021

Evidence of the Advantages of Preoperative Intra-aortic Balloon Pump in Surgical Revascularization of Acute Myocardial Infarction

Patients hospitalized due to acute myocardial infarction (AMI) and scheduled for coronary artery bypass grafting (CABG) surgery based on the decision of the Cardiology and Cardiovascular Surgery council will be included in this prospective observational cohort study. Based on their clinical conditions, the patients will be categorized into two groups: Group A, comprising those receiving intra-aortic balloon pump (IABP) support, and Group B, comprising those not receiving IABP support.

The patients' anamnesis, medical history, physical examination findings, laboratory results, and EuroScore-II scores will be meticulously recorded. Details of the assessments are as follows:

Assessment of Chest Pain (Angina): Chest pain severity will be evaluated on the first day of admission using a scoring system based on the Wong-Baker FACES® pain scale (0–10; Wong-Baker FACES Foundation; https://wongbakerfaces.org). For patients in the IABP group, pain severity will also be recorded immediately before IABP placement and at 12 and 24 hours post-implantation.

Laboratory Studies: The following parameters will be analyzed: hemoglobin (g/dL), hematocrit (%), platelet count, troponin (ng/mL), CK-MB (U/L), LDL (mg/dL), C-reactive protein (CRP, mg/L), glycated hemoglobin (HbA1c, %), and creatinine (mg/dL). High-sensitivity cardiac troponin I (hsCTI) levels will be measured, with the reference range of 0–0.04 ng/mL for both genders, as per our hospital's laboratory standards. hsCTI levels will be checked at admission and subsequently every 24 hours for both groups until the patient undergoes surgery.

Echocardiography (ECHO): On the first day, ECHO will be performed to assess ventricular function, ejection fraction (EF%), valve pathologies, and any ventricular abnormalities such as aneurysm or ventricular septal rupture. Follow-up ECHO will be conducted during the early postoperative period and at the first-month follow-up after discharge to reassess EF% and identify any pericardial effusion.

Patients who demonstrate a decline in hsCTI levels or experience recurrent chest pain attacks will undergo coronary artery bypass grafting (CABG). All surgical procedures will be performed by the same surgical team using a standardized approach. Surgical Approach: The surgeries will be conducted via a median sternotomy under cardiopulmonary bypass (CPB). Complete revascularization will be achieved with the application of an aortic cross-clamp (ACC), guided by the vascular anatomy identified during angiography. Assessment of Graft

Flow: Following the removal of the ACC and the termination of CPB, transit-time flow measurement (TTFM) will be employed to evaluate the graft flow rates, ensuring optimal surgical outcomes.

In the postoperative period, the following parameters will be recorded: Mechanical Ventilation Duration (MV): Measured in hours from the patient's admission to the intensive care unit (ICU) until the cessation of mechanical ventilation. Bleeding Volume: The total amount of bleeding in milliliters during the first 24 hours postoperatively. Length of Stay in the Intensive Care Unit (ICU): The duration (in days) from the postoperative phase until the patient is transferred to the general ward. Total Length of Hospital Stay (HS): The number of days from hospital admission to discharge. Low Cardiac Output Syndrome (LCOS): LCOS will be defined as the presence of the following criteria: Requirement for high-dose positive inotropic agents (e.g., adrenaline, dobutamine, or noradrenaline) administered via continuous infusion, lactic acidosis (lactate levels >4 mmol/L), persistent hypotension and decreased or absent urine output. In-Hospital Mortality: Any death occurring within 30 days postoperatively will be classified as in-hospital mortality.

Exclusion criteria

To ensure a homogeneous distribution of risk factors between the groups and to accurately evaluate the effect of IABP on troponin levels, the following patients will be excluded from the study:

• Patients requiring emergency surgery due to iatrogenic cardiac or coronary injuries caused by angiography.

• Patients with mechanical complications of acute myocardial infarction, such as chordae rupture or ventricular septal rupture.

• Patients undergoing surgery using the off-pump or pumped beating heart method.

- Patients with peripheral arterial disease.
- Patients with renal failure.
- Patients with a history of cerebrovascular accidents.
- · Patients presenting with acute cardiogenic shock or cardiac arrest

Preoperative IABP Application and Indications:

The primary indications for intra-aortic balloon pump (IABP) application in patients include elevated troponin levels and recurrent or persistent chest pain at rest.

Other common indications are:

- Hemodynamic instability.
- Multivessel coronary artery disease.
- Left main coronary artery disease.
- Narrow and/or tortuous coronary artery anatomy where percutaneous coronary intervention (PCI) has failed or is not feasible.

Procedure:

The IABP catheter is typically inserted into the femoral artery by cardiovascular surgeons under local anesthesia. The placement of the catheter is confirmed either in a hybrid operating room or using a portable imaging scope.

Statistical Analysis

The research will be conducted utilizing IBM SPSS 24 (IBM, Armonk, NY, USA) software and R-project version 4.2.3 for statistical analysis. The statistics will be provided in terms of mean, standard deviation, median, minimum, maximum, percentage, and count. After testing for normality, baseline characteristics of the two groups will be compared using Student's t-test or the Mann–Whitney U-test for continuous variables and chi-square or Fisher's exact tests for categorical variables. Differences between the IABP group and the control group regarding repeatedly measured outcomes will be analyzed using mixed ANOVA. The prognostic value of risk factors for in-hospital mortality will be evaluated by multivariate logistic regression analysis. The propensity score will be computed using a logistic regression model, incorporating the following covariates: age, gender, creatinine, CK-MB, hs-CTI levels, preoperative LVEF, and EuroScore II. The statistical significance level will be set at p<0.05.

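### No hsCTI draw is tied to IABP insertion and Group B has no counterpart to that time, so draws taken before a late insertion would be analysed as IABP follow-up

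*Combined protocol and SAP*

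**What the plan says.** The opening study description forms the groups according to clinical condition: "Group A, comprising those receiving intra-aortic balloon pump (IABP) support, and Group B, comprising those not receiving IABP support". It gives no time at which a patient is classed.

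Under Laboratory Studies, "hsCTI levels will be checked at admission and subsequently every 24 hours for both groups until the patient undergoes surgery". The hsCTI clock therefore starts at admission in both groups and stops at surgery.

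The only measurement tied to insertion is the pain score, in Group A alone. Under Assessment of Chest Pain, "pain severity will also be recorded immediately before IABP placement" and again 12 and 24 hours afterwards. Group B has a pain score on the first day only.

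Under Preoperative IABP Application and Indications, the primary indications "include elevated troponin levels and recurrent or persistent chest pain at rest". On surgery, the plan says: "Patients who demonstrate a decline in hsCTI levels or experience recurrent chest pain attacks will undergo coronary artery bypass grafting (CABG".

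Under Statistical Analysis, "Differences between the IABP group and the control group regarding repeatedly measured outcomes will be analyzed using mixed ANOVA". The propensity score includes hs-CTI without saying which draw. The Exclusion criteria give, as one reason for the exclusions, the wish "to accurately evaluate the effect of IABP on troponin levels".

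**The concern.** A device can change troponin only from the moment it is inserted. A label fixed per patient, applied to a series that starts at admission, treats every draw after admission as exposed, including any taken before the balloon was in place. Three consequences follow if insertion comes late in some patients.

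- **Dilution.** Unexposed draws in Group A pull a real difference towards zero.
- **Selection into groups.** A fall in hsCTI leads to surgery, and a patient operated on before any insertion belongs to Group B. A draw taken before exposure can then help to decide the group, and early decliners may collect in Group B.
- **Adjustment for a consequence.** If the propensity-score hs-CTI comes after insertion, the score conditions on something that the device may already have changed.

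At stake is the between-group hsCTI comparison, the only measure with a repeated preoperative schedule in both groups.

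**Working it through.** The plan states no insertion delay, sample size or effect size, so there is no figure to reproduce. All numerical inputs below are assumptions, chosen to show the mechanism.

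**1. Can a post-admission draw precede insertion?** Recurrent rest pain is an indication and can arise after admission. No passage requires insertion before the 24-hour draw, and none says that it comes later. Both are compatible with the text.

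**2. How many draws would be unexposed?** With insertion h hours after admission, the number of unexposed post-admission draws is the whole number of 24-hour periods in h. Divide by the number of post-admission draws before surgery for the share.

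| Insertion (assumed) | Unexposed draws | Share if 3 / 4 / 5 draws |
|---|---|---|
| 6–23 h | 0 | 0 / 0 / 0 |
| 25–36 h | 1 | 33% / 25% / 20% |
| 49 h | 2 | 67% / 50% / 40% |

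**3. Dilution.** Let e be the effect on log hsCTI per 24 hours of exposure. Let p be the share of Group A inserted just after the 24-hour draw, unrelated to hsCTI. With a fixed label, the A−B difference in change from admission is (1 − p)e at 24 h and (2 − p)e at 48 h. With e = −0.20:

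| p | 24 h | 48 h |
|---|---|---|
| 0 | −0.20 | −0.40 |
| 0.5 | −0.10 | −0.30 |
| 1 | 0.00 | −0.20 |

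A simulation of 400,000 patients per scenario gave the same values.

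**4. Selection, with no true effect.** Assume that the 24-hour log change has mean −0.35, between-patient SD 0.25 and SD 0.15 per draw. Its SD is √(0.25² + 2 × 0.15²) = 0.328. Suppose late insertions occur only among the half of patients whose hsCTI falls by less than average. Their mean excess is 0.798 × 0.328 = 0.262.

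- All insertions late, 30% of patients in Group A: difference = 0.262 + 0.262 × 0.3/0.7 = +0.374 (simulated +0.374).
- Mixed timing: 15% of patients are inserted early at random, then 30% of the eligible half of the remaining 85%, that is 0.5 × 0.30 × 0.85 = 0.1275. Group A is 0.15 + 0.1275 = 0.2775 of patients, and 0.1275/0.2775 = 46% of its insertions are late. Difference = 0.262 × 0.1275 × (1/0.2775 + 1/0.7225) = +0.17 (simulated +0.165).
- The same mixed timing with a true e of −0.20: add −0.20 × 0.15/0.2775 = −0.108, giving about +0.06 (simulated +0.057). A benefit would appear as slight harm.
- No late insertions: 0.00.

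**5. Is the sign fixed?** Steps 3 and 4 both work against the device, but only under their assumptions. Recurrent pain is a reason for surgery as well as for a balloon, so patients doing badly may also reach surgery without one and enter Group B. That would push the other way. The documents do not say how often either route is taken.

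**The case against.** The strongest reply is that the harm rests on a condition that the plan never states. Inclusion follows the council's decision for CABG, and the grouping is described in the very next sentence. Left main disease, multivessel disease and failed or unfeasible PCI are anatomical indications, and troponin can be high on arrival. Early insertion fits the text as well as late insertion does, and with every balloon in before the 24-hour draw the problem all but disappears. This stands, and the point is conditional for that reason.

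The plan also does not list which draws enter the mixed ANOVA or its time origin. That pre-insertion draws count as follow-up is inferred from a fixed group factor and an admission-based series. The inference is natural, and no rule in the plan prevents it.

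A reader might go further in several ways that the documents do not support:

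- **That insertion is in fact delayed**, because pain is scored just before placement. That score allows for a delay but does not show one.
- **That Group B has no time origin.** Admission is a common sampling clock, and the admission draw can serve as a baseline. What is missing is a counterpart to the insertion time.
- **That troponin is the primary aim.** The aim is stated only as a reason for the exclusions, and no primary outcome is named.
- **That length of stay is biased too.** Total stay is defined as "The number of days from hospital admission to discharge", so it includes the preoperative wait. But no waiting times are given and no between-group test of total stay is named. Outcomes counted from surgery are not touched by mislabelled draws.

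**Conclusion.** The gap is real and worth closing before analysis: the plan as written can give a biased hsCTI contrast, and nothing in it lets a reader tell whether it does. The conclusion rests on the fixed group label, the admission-based hsCTI series and an indication that can arise after admission. It takes effect only if some insertions follow the 24-hour or a later draw.

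The figures above illustrate the mechanism and do not estimate bias in this study. A reader might take them to show that the comparison is biased against the IABP; the documents fix neither size nor sign. Choosing patients for a balloon because their troponin is high is a separate problem, confounding by indication, and would remain even with a perfect index time.

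**What to change.** - Record the times of admission, insertion and surgery.
- In Group A, take the last hsCTI at or before insertion as both the baseline and the propensity-score value. Do not count earlier draws as IABP follow-up.
- In Group B, take the draw at a comparable time since admission, among patients still awaiting surgery without a balloon. State how a comparator who later receives one is handled.
- Compare later hsCTI with a mixed model that allows unequal series length and adjusts for that baseline.
- Risk-set matching or marginal structural weighting may be a sensitivity analysis; neither is needed to close the gap.

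**Cost.** SAP wording, three recorded times and slightly more analysis. Insertion time is already needed for the 12- and 24-hour pain scores. If all insertions prove to be early, the Group A baseline is simply the admission draw. On a 24-hour schedule the baseline can be up to 24 hours old at insertion. Some patients operated on early may have no comparator. Recurrent pain before the index time can be added as a covariate only if it is dated in both groups, which means extra data collection in Group B. Confounding by indication, for example through haemodynamic instability or coronary anatomy, remains.

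### hsCTI is timed only from admission and symptom-onset time is not used, so a group difference in infarct age could pass for an IABP effect on troponin

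*Combined protocol and SAP*

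**What the plan says.** The combined protocol and SAP fixes the troponin schedule under Laboratory Studies: "hsCTI levels will be checked at admission and subsequently every 24 hours for both groups until the patient undergoes surgery". Time zero is therefore hospital admission for every patient.

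Entry is open to "Patients hospitalized due to acute myocardial infarction (AMI) and scheduled for coronary artery bypass grafting (CABG) surgery". No window from symptom onset is given there, and none of the exclusions limits infarct age. Allocation is not random: "Based on their clinical conditions, the patients will be categorized into two groups". On indications, the section on preoperative IABP states: "The primary indications for intra-aortic balloon pump (IABP) application in patients include elevated troponin levels and recurrent or persistent chest pain at rest".

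The Exclusion criteria section says that the exclusions are there partly "to accurately evaluate the effect of IABP on troponin levels", so the troponin course is a stated target of the study.

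Under Statistical Analysis, repeatedly measured outcomes are compared between groups by mixed ANOVA, with no covariate named. The propensity score has seven covariates: "age, gender, creatinine, CK-MB, hs-CTI levels, preoperative LVEF, and EuroScore II". Time from onset is not among them. The plan does not say which hsCTI measurement enters the score, how the score will be used, or whether it bears on the mixed ANOVA at all.

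The history items to be collected are general: "anamnesis, medical history, physical examination findings, laboratory results, and EuroScore-II scores will be meticulously recorded". Onset time may be captured there, but it is not named and no analysis uses it.

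**The concern.** After an infarct, troponin climbs, peaks and declines without any intervention. A patient admitted a few hours after onset may still be rising at the 24 h draw. A patient admitted a day after onset is probably already falling. On an admission clock these two look like different responses to care.

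In a randomized trial, infarct age would balance on average. Here the groups follow from clinical condition, and two of the named indications, raised troponin and continuing pain, themselves depend on where the patient stands in the infarct. The plan neither balances infarct age nor collects anything by name that would reveal an imbalance.

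What is at stake is the reading of the troponin result. A steeper fall in the IABP group could mean that its patients were later in their natural course at admission, and a shallower fall that they were earlier. Aligning draws to balloon insertion would not settle this, because infarct age would still shape the curve.

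**Working it through.** The plan gives no troponin effect size, sample size or delay distribution, so there is no figure of its own to reproduce. The check has a textual part and two illustrations. All kinetics and delays below are assumptions.

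**1. Where onset time could enter.** Eligibility: absent. Exclusions: absent. hsCTI schedule: counted from admission. Mixed ANOVA: no covariate. Propensity score: seven covariates, onset time not one of them. History: possible, but not named.

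**2. Single-patient ratios with no IABP effect.** Let C(t) = exp(−ke·t) − exp(−ka·t), with t in hours since onset, ke = ln 2 / half-life, and ka solved so that ln(ka/ke)/(ka − ke) equals the peak time. For a patient admitted d hours after onset, R(d) = C(d + 24)/C(d). The grid is half-life 18, 24 or 36 h crossed with peak at 12, 18 or 24 h.

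Middle case (half-life 24 h, peak 18 h): ke = 0.0289, ka = 0.0951.
- R(6) = 0.3627/0.2756 = 1.32
- R(12) = 0.3209/0.3876 = 0.83
- R(18) = 0.67
- R(24) = 0.2396/0.3979 = 0.60
- R(48) = 0.52

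The reduction for the later-admitted patient is 1 − R(later)/R(earlier):

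| Delays compared | Middle case | Range over the nine curves |
|---|---|---|
| 12 vs 18 h | 19% | 6-22% |
| 12 vs 24 h | 27% | 8-33% |
| 24 vs 48 h | 14% | 1-25% |
| 6 vs 24 h | 54% | 29-60% |

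The last row uses the steep early part of the curve and compares two individuals. It is not an estimate of a group bias.

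**3. Why one troponin value is a weak proxy.** In the middle case C(6) = 0.2756, and the same height recurs at about 42.5 h. The 24 h ratios from those two points are 1.32 and 0.53, so the same admission value can precede a rise or a halving.

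**4. Group simulation with no IABP effect.** Assumptions:
- 50 patients per group, 600 replicates.
- Median onset-to-admission delay 12 h in controls, shifted in the IABP group; log-scale SD 0.5.
- Peak/half-life 15/18, 18/24 or 24/36 h.
- Log-normal infarct size (log SD 0.8) and measurement noise (log SD 0.1).
- CK-MB with peak 16 h, half-life 12 h and extra noise (log SD 0.3).

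The outcome is the 0-24 h change in log hsCTI. With two time points, its unadjusted comparison is the group-by-time test of a mixed ANOVA. Entries are the IABP/control ratio of change, with the share of replicates at p<0.05 in brackets, over the three curves.

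| Shift in IABP median delay | Unadjusted | Adjusted for admission hsCTI and CK-MB | Also adjusted for onset time |
|---|---|---|---|
| −6 h | 1.57-1.59 (100%) | 1.46-1.53 (100%) | 1.00 (5-6%) |
| 0 | 1.00 (5-6%) | 1.00 (5-7%) | 1.00 (5-6%) |
| +6 h | 0.81-0.82 (92-94%) | 0.82-0.85 (79-92%) | 1.00 (4-5%) |
| +12 h | 0.72-0.73 (100%) | 0.73-0.79 (100%) | 1.00 (4-6%) |
| +24 h | 0.64-0.66 (100%) | 0.66-0.72 (100%) | 0.99-1.00 (4-6%) |

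With no shift there is no bias. With a shift, linear adjustment for the two markers leaves most of it. The last column is a best case, because onset was known without error (entered as log delay and its square).

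**The case against.** **No imbalance is shown.** A reader might infer that the IABP group is later, or earlier, in the infarct and that the troponin result is therefore biased. The documents do not support that. They give no delays, and the PCI-related indication concerns coronary anatomy, not hours since onset. This stands: the point is conditional and its direction unknown.

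**The largest contrast is not a group effect.** For 29-60% to apply between groups, the whole of one group would have to be admitted at 6 h and the whole of the other at 24 h. Patients already referred by a council for CABG need not be early presenters. This also stands, and the smaller contrasts belong beside it.

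**Serial draws reveal the phase, and CK-MB is a second marker.** A reader might infer that an IABP effect can never be separated from natural kinetics. That is too strong, since patients with two or more draws show whether they are rising or falling. However, those later draws are the outcome being compared, so they cannot also serve as the baseline adjustment. CK-MB helps somewhat. The simulation tests only one assumed CK-MB curve and a linear adjustment, so how much bias remains after adjustment is uncertain.

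**One onset and one curve may not fit.** Recurrent or persistent pain is itself an IABP indication, so onset may be harder to date in Group A and a single rise and fall may not describe these patients. This stands, and it argues against making onset the only time axis.

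**Some remedies would miss.** The score is never tied to the mixed ANOVA, so adding onset delay to the score alone need not change the troponin comparison. Hours since onset are irregular and do not fit a mixed ANOVA with common time levels. Restricting to patients admitted more than 24 h after onset leaves up to 25% (24 vs 48 h). All three limits stand.

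**Conclusion.** The concern holds as a conditional one. It follows from the documents that hsCTI is counted only from admission, that time from onset is used nowhere in selection or analysis, and that groups are formed by clinical condition while an effect on troponin is a stated target. If infarct age at admission differs, natural kinetics could account for part or all of an apparent IABP effect, in either direction.

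Confidence is high for the omission and much lower for its size. Single-patient differences range from 1% to 60% across the contrasts examined. In the simulation, median shifts of 6 to 24 h later gave spurious ratios of 0.64-0.82, and a shift of 6 h earlier gave 1.57-1.59. The rejection rates depend further on the assumed 50 per group and noise levels. The omission is worth correcting without proof of imbalance, because a strong determinant of the outcome should be measured in a non-randomized comparison.

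**What to change.** - Record symptom-onset date and time for both groups, taken from the anamnesis. Flag patients whose onset is uncertain or whose pain was recurrent. Record the actual time of each hsCTI draw.
- Report onset-to-admission time by group, so that any imbalance is visible.
- Replace the unadjusted mixed ANOVA for hsCTI with a linear mixed model, or an ANCOVA of the 24 h value. In the mixed model, include onset-to-admission time and its interaction with time, allowing for curvature (for example log delay and its square). The interaction is needed because delay alters the slope; a main effect alone would leave the group-by-time contrast exposed.
- Add onset-to-admission time to the propensity score as well, and state which hsCTI measurement enters the score and how the score is used.
- As optional sensitivity analyses: hours since onset as the time axis; patients admitted more than 24 h after onset; exclusion of patients with flagged onset. The 24 h restriction reduces the problem but does not remove it.

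The cost is a chart field with a flag, draw times, and a different model; no extra samples are needed. The downsides are that onset time is imprecise when pain recurs, possibly more so in the IABP group, which could add differential error, and that one more covariate and its interaction are spent in a study whose size the plan does not state.

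### The last EF reading is dated from discharge rather than surgery, so its postoperative timing follows the length of the postoperative stay and can differ between the non-randomised groups

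*Combined protocol and SAP*

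**What the plan says.** EF is scheduled three times. For the baseline, the Echocardiography (ECHO) paragraph has "On the first day, ECHO will be performed to assess ventricular function, ejection fraction (EF%), valve pathologies". For the later readings it has "Follow-up ECHO will be conducted during the early postoperative period and at the first-month follow-up after discharge to reassess EF". The early postoperative reading has no stated day. The last is placed relative to discharge.

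The list of postoperative parameters includes "Total Length of Hospital Stay (HS): The number of days from hospital admission to discharge". ICU stay is recorded as well. Death is counted from a different origin: "Any death occurring within 30 days postoperatively will be classified as in-hospital mortality".

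On grouping, the opening paragraph says "Based on their clinical conditions, the patients will be categorized into two groups". On analysis, the Statistical Analysis section says "Differences between the IABP group and the control group regarding repeatedly measured outcomes will be analyzed using mixed ANOVA". It does not list those outcomes, and it gives no rule for unequal timing, missing readings or death before a reading. The propensity model uses age, gender, creatinine, CK-MB, hs-CTI, preoperative LVEF and EuroScore II.

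**The concern.** A mixed ANOVA treats each visit as one level of a time factor shared by everyone. The last EF level does not have that property. Two patients operated on the same day and discharged a week apart have their final ECHO a week apart, yet both count as the same time point.

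This would be little more than noise if postoperative stay were alike in the two groups. There is no reason to expect that. Grouping follows clinical condition, and the listed IABP indications include hemodynamic instability and persistent pain at rest. IABP may also itself change recovery. The time of measurement is therefore settled after exposure, and a score built from preoperative covariates cannot adjust for it. If EF is still changing in the weeks after surgery, the group with the longer postoperative stay is read further along that course, and the difference is counted as a group effect. The direction cannot be known in advance.

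**Working it through.** The documents give no sample size, EF effect, slope or expected stay, so there is no planned figure to reproduce. The check is a reading of the schedule followed by illustrations on assumed inputs.

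**1. Is EF in the mixed ANOVA?** It is not named. By schedule:
- Pain scores are repeated only in the IABP group.
- hs-CTI is repeated in both groups but stops at surgery.
- EF is the only outcome scheduled in both groups both before and after surgery.

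Including EF is therefore a reasonable inference, not a stated fact.

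**2. When does the last reading fall?** Day after surgery = postoperative stay + 30, taking a month as 30 days (assumption). Assumed postoperative stays of 5, 7, 10, 14 and 21 days give days 35, 37, 40, 44 and 51. The spread between the extremes is 51 − 35 = 16 days.

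**3. What does a group gap do to mean EF?** Shift = group difference in mean postoperative stay × EF slope. Slopes and gaps are assumptions.

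| Assumed EF slope | Gap (days) | Shift (EF points) |
|---|---|---|
| 0.5 per 30 days | 2 / 5 / 10 | 0.03 / 0.08 / 0.17 |
| 1 per 30 days | 2 / 5 / 10 | 0.07 / 0.17 / 0.33 |
| 2 per 30 days | 2 / 5 / 10 | 0.13 / 0.33 / 0.67 |
| 0.05 per day (1.5 per 30 days) | 3 / 7 | 0.15 / 0.35 |
| 0.15 per day (4.5 per 30 days) | 3 / 7 | 0.45 / 1.05 |

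The range is about 0.03 to 1 point. Pairing the steepest slope with the widest gap gives 0.15 × 10 = 1.5, but that takes both extremes at once. Against an assumed EF standard deviation of 10, a shift of 0.67 is 0.067 SD and 1.05 is 0.105 SD.

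**4. Which part of the stay counts?** Recorded hospital stay runs from admission, so it equals preoperative wait + postoperative stay. Only the second term enters step 2. A group difference lying wholly in the wait for surgery would not move the reading relative to surgery.

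**5. Separate matter: who has a last reading?** A simulation with no true EF difference (mean 45, SD 10), mortality pairs of 2% v 5%, 2% v 10% and 5% v 15%, and odds of death 1.5 or 2 times higher per SD lower EF gave survivors-only differences of 0.14 to 0.65 points, favouring the group with more deaths. All these inputs are assumed. The effect comes from death, not from the visit anchor.

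**The case against.** The best case against is that a visit a month after discharge is ordinary follow-up in an observational cohort, that it also serves to look for pericardial effusion, and that no EF endpoint or one-month EF hypothesis is stated. The exclusion criteria name troponin as the effect of interest. On the assumptions above the bias is small. All of this stands, and it is why the point is a refinement and not an error in the plan. The wording might also mean a visit in the first month that merely falls after discharge. If so, the sentence is ambiguous and needs the same clarification.

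Several stronger readings are tempting, and the documents do not support them:
- *Hospital stay is a compared outcome.* It is listed as recorded, and the Statistical Analysis section names no test for it. Comparison is a natural inference in a two-group study, no more.
- *Any group difference in total hospital stay biases EF.* Only the postoperative part does.
- *Patients with a long stay have no last reading.* With a discharge anchor, a long-stay survivor is read late. Only death or non-attendance removes the reading.
- *The discharge anchor causes the selection of survivors.* A fixed postoperative day would equally have no EF for patients who died before it.

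What remains is the timing itself. It is systematic, it is set after exposure, and neither the ANOVA nor the propensity score handles it.

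**Conclusion.** The point holds as a low-priority improvement. On the plain reading, time from surgery to the last EF is the postoperative stay plus about a month, and it can differ between groups that were not randomised. If EF enters the mixed ANOVA, part of any difference at the last time point may reflect recovery time.

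The size is roughly 0.03 to 1 EF point in the group mean. It approaches the upper end only if postoperative stays differ by about a week and EF changes at the steepest slope assumed. These figures rest on assumed slopes, gaps and a 30-day month; the documents supply none of them. A reader might infer that the timing alone could produce or conceal an important EF effect. A bias of this size does not support that, although individual patients may be read more than two weeks apart.

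**What to change.** Replace the discharge anchor in the Echocardiography (ECHO) paragraph with one fixed postoperative day and a stated window, the same in both groups, with the ECHO done in hospital if the patient has not yet gone home. Mortality is already counted from surgery, so EF and survival would then share an origin. State in the Statistical Analysis section whether EF is among the outcomes analysed by mixed ANOVA.

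Record the actual days from surgery to each ECHO and summarise them by group. Keep that interval out of the main model: it is determined after exposure, so adjusting for it could condition on a consequence of IABP, and within a tight window it would vary little anyway. A sensitivity analysis is the right place for it. If readings have already been taken, the surgery and ECHO dates allow the same summary.

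Separately, report by group the deaths and missed visits before the last reading, and state how the analysis treats patients without it. A classical mixed ANOVA on complete cases would also discard their earlier readings. Re-dating the visit does not solve this.

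The cost is one changed sentence, one extra recorded interval and a few in-hospital ECHOs. The visit moves by some days for some patients and may no longer coincide with routine post-discharge follow-up.
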